#### **6.2.4. Additional considerations**

To explore the correlation between anti-H1 HA stalk ELISA and anti-H1 HA stalk MN a scatter plot of ELISA antibody results to the H1 stalk with the micro-neutralizing antibody and results to the H1 stalk at all timepoints will be presented in log scale.

The same analysis will be done to explore the correlation:

- Between anti-H1 HA stalk ELISA and HI against ch5/1N1 and ch8/1N1
- Between anti-H1 HA stalk ELISA and anti-H1 stalk ADCC
- Between anti-H1 HA stalk ELISA at different timepoints

Upon availability of test results from tertiary endpoints not included in [Table 2](#) (e.g. ADCC, total plasmablasts), a descriptive analysis will be done for the timepoints analyzed.

### **6.3. Analysis of safety**

The analysis will be performed on the ES.

All analyses will be descriptive. Data will be presented by dose, overall/dose and overall/subject. Outputs will be presented by study group. Analyses will be repeated pooling groups according to the adjuvant (AS01, AS03, no adjuvant).

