## 2. STUDY DESIGN

\*If a subject presents signs and symptoms of influenza-like illness (ILI), nasal and throat swabs will be collected as soon as possible (preferably within 24 hours, but not later than 7 days) after the onset of an ILI to test for influenza and/or other respiratory pathogens by RT-PCR **if deemed necessary or for storage**.

\*\*IDMC reviews will be performed throughout the study.

- **Experimental design:** Phase I/II, observer-blind, randomized, controlled, multi-centric study with 10 parallel groups.
- **Study groups:**
  - **cH8/P/cH5-AS03 group:** 47 subjects receiving one dose of cH8/1N1+AS03 at Day 1, one dose of PBS at Day 57 and one booster dose of cH5/1N1+AS03 at Month 14.
  - **cH5/P/cH8-AS03 group:** 47 subjects receiving one dose of cH5/1N1+AS03 at Day 1, one dose of PBS at Day 57 and one booster dose of cH8/1N1+AS03 at Month 14.
  - **cH8/5/11-AS03 group:** 47 subjects receiving one dose of cH8/1N1+AS03 at Day 1, one dose cH5/1N1+AS03 at Day 57 and one booster dose of cH11/1N1+AS03 at Month 14.
  - **cH8/P/cH5-AS01 group:** 47 subjects receiving one dose of cH8/1N1+AS01 at Day 1, one dose of PBS at Day 57 and one booster dose of cH5/1N1+AS01 at Month 14.
  - **cH5/P/cH8-AS01 group:** 47 subjects receiving one dose of cH5/1N1+AS01 at Day 1, one dose of PBS at Day 57 and one booster dose of cH8/1N1+AS01 at Month 14.
  - **cH8/5/11-AS01 group:** 47 subjects receiving one dose of cH8/1N1+AS01 at Day 1, one dose cH5/1N1+AS01 at Day 57 and one booster dose of cH11/1N1+AS01 at Month 14.
  - **cH8/P/cH5 group:** 47 subjects receiving one dose of cH8/1N1 at Day 1, one dose of PBS at Day 57 and one booster dose of cH5/1N1 at Month 14.
  - **cH5/P/cH8 group:** 47 subjects receiving one dose of cH5/1N1 at Day 1, one dose of PBS at Day 57 and one booster dose of cH8/1N1 at Month 14.
  - **cH8/5/11 group:** 47 subjects receiving one dose of cH8/1N1 at Day 1, one dose cH5/1N1 at Day 57 and one booster dose of cH11/1N1 at Month 14.
  - **IIV4 group:** 47 subjects receiving one dose of *Fluarix Quadrivalent* at Day 1, one dose of PBS at Day 57 and one dose of *Fluarix Quadrivalent* at Month 14.
- **Treatment allocation:** randomized (1:1:1:1:1:1:1:1:1 ratio) using GSK Biologicals' Randomization System on Internet (SBIR). The randomization algorithm will use a minimization procedure accounting for center, sex, age (18-30 years vs. 31-39 years) and history of influenza vaccination since the 2014/2015 season (yes vs. no).

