### 12.2.2. Dose number

The study dose number is defined in reference to the number of study visits at which vaccination occurred. More specifically dose 2 refers to all vaccines administered at the second vaccination visit while dose 3 corresponds to all vaccinations administered at the third vaccination visit even if dose 2 was not administered to the subject.

The relative dose for an event (AE, medication, vaccination) is the most recent study dose given before an event. In case the event takes place on the day a study dose is given, the related dose will be that of the study dose, even if the event actually took place before vaccination. For instance, if an adverse event begins on the day of the study vaccination but prior to administration of the vaccine, it will be assigned to this dose. In case a study dose is not administered and an event occurs after the subsequent study dose (e.g. 3rd study dose), the relative dose of the event will be study dose associated to the subsequent study dose (e.g. dose 3).

The number of doses for a product is the number of time the product was administered to a subject.

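### Safety tables pooled by adjuvant count PBS injections under the adjuvant label: 67% of each pooled Dose 2 row, and 33% (Day 85) or 22% (final) of overall/dose

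*SAP*

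**What the plan says.** SAP Amendment 3, section 6.3, sets the layout for safety: "Data will be presented by dose, overall/dose and overall/subject". Outputs are by study group first, and then: "Analyses will be repeated pooling groups according to the adjuvant (AS01, AS03, no adjuvant". The unit pooled is the group, not the product given at a visit.

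Section 2 gives each adjuvant class three groups of 47. In the AS03 class, cH8/P/cH5-AS03 and cH5/P/cH8-AS03 each receive "one dose of PBS at Day 57". Only cH8/5/11-AS03 receives vaccine at that visit: "47 subjects receiving one dose of cH8/1N1+AS03 at Day 1, one dose cH5/1N1+AS03 at Day 57". The AS01 class follows the same pattern (its first group reads "47 subjects receiving one dose of cH8/1N1+AS01 at Day 1, one dose of PBS at Day 57"), and so does the non-adjuvanted class.

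The vaccination schedule in section 2 calls Day 57 a primary dose without exempting any group. Section 12.2.2 numbers doses by visit: "dose 2 refers to all vaccines administered at the second vaccination visit". Templates 15 and 24 use administered doses as the denominator, and Templates 16 and 17 use documented doses. None of them carries a provision for PBS.

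**The concern.** The purpose of repeating safety by pooled adjuvant is to characterise what each adjuvant does. A row headed AS03, Dose 2 will be read as reactogenicity after a second AS03-adjuvanted dose. As the plan is written, most people in that row received PBS at that visit. The overall/dose row carries the same mixture in smaller proportion.

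If PBS causes fewer reactions than vaccine, both rows understate reactogenicity after adjuvanted vaccine and compress the contrast with the non-adjuvanted class. The Dose 2 confidence interval would also be computed on about 141 subjects, so the wrong quantity would look precisely estimated. Solicited and unsolicited events after each vaccine dose are primary endpoints (section 4.1), so a summary of them should contain what its label says.

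**Working it through.** **Check on group sizes.** 10 groups × 47 = 470, which agrees with the approximate total in Table 2 of the SAP. The plan states no figure for the PBS share of a pooled column.

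**Is the PBS injection counted as dose 2?** The SAP does not say so in one sentence, but its usage points that way:
- The section 2 schedule calls Day 57 a primary dose for all groups.
- Code 2080 (section 5.2.2.2) applies a 56–66 day window from dose 1 to dose 2 to subjects in general.
- Code 2090 (section 5.2.2.3) times Visits 6, 7 and 8 from dose 2. In the seven groups given PBS, dose 2 can only be the PBS injection.
- Section 12.2.2 numbers doses by vaccination visit.

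**PBS share per pooled adjuvant class** (3 × 47 = 141 subjects, of whom 2 × 47 = 94 receive PBS at Day 57):

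| Row | PBS / total | Share |
|---|---|---|
| Dose 1 | 0/141 | 0% |
| Dose 2 | 94/141 | 66.7% |
| Dose 3 | 0/141 | 0% |
| Overall/dose, Day 85 analysis | 94/282 | 33.3% |
| Overall/dose, final analysis | 94/423 | 22.2% |

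These shares apply where the denominator is doses given or documented (Templates 15–17 and 24). In Template 18 the denominator is doses with the symptom, so the PBS share there depends on the reaction rates.

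**Effect on a rate.** Let a be the rate after vaccine (taken as the same at each dose) and p the rate after PBS.
- Dose 2 = (a + 2p)/3
- Overall/dose, Day 85 = (4a + 2p)/6
- Overall/dose, final = (7a + 2p)/9

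The SAP gives no reaction rates, so a and p are assumptions:

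| a | p | Dose 2 | Overall/dose, Day 85 | Overall/dose, final |
|---|---|---|---|---|
| 50% | 5% | 20.0% | 35.0% | 40.0% |
| 50% | 30% | 36.7% | 43.3% | 45.6% |
| 70% | 10% | 30.0% | 50.0% | 56.7% |
| 90% | 10% | 36.7% | 63.3% | 72.2% |
| 90% | 30% | 50.0% | 70.0% | 76.7% |

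For a = 90% and p = 10%, with counts rounded to whole subjects, the Clopper-Pearson 95% interval is 77–97% on the 47 vaccine recipients and 28–45% on the pooled 141.

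**Effect on the contrast.** With the same p in both classes, the Dose 2 difference is (a₁ + 2p)/3 − (a₀ + 2p)/3 = (a₁ − a₀)/3. A true 60-point difference appears as 20 points, whatever p is. By the same algebra, overall/dose keeps 4/6 of the difference at Day 85 and 7/9 at the final analysis.

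**If IIV4 were placed in the no-adjuvant class**, which the SAP neither says nor rules out, the PBS share of that Dose 2 row would be 141/188 = 75%.

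**Comparison with immunogenicity.** Template 37 also pools by adjuvant, but takes Day 29 from the one-priming-dose groups and Day 85 only from cH8/5/11. Response to priming is therefore never read after a PBS injection. Section 6.3 has no counterpart.

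**The case against.** **The information is not lost.** Section 6.3 requires by-group outputs first. The Dose 2 rows for cH8/5/11-AS03, cH8/5/11-AS01 and cH8/5/11 show second-dose vaccine reactogenicity with no PBS, and section 11 puts the PBS injection in the label and footnote definition of each group that receives it. This stands. It limits the defect to the pooled repeat and to overall/dose; it does not make the pooled rows correct.

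**The adjuvant contrast survives elsewhere.** Every investigational group receives its assigned formulation at Day 1 and Month 14, so the pooled Dose 1 and Dose 3 comparisons are clean. Overall/subject counts a subject who reacted at least once, so it is not diluted in this way. This stands too.

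**PBS may not count as study vaccine.** Table 4 bases its denominators on study vaccine administered, and on that reading PBS visits might drop out. The schedule, the windows timed from dose 2 and the dose-numbering rule point the other way. Even on the contrary reading the denominator would need a rule.

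**The list of tables might deal with it.** Section 13 lets titles and footnotes be adapted as that list indicates, and the list is not shown. A footnote there would improve labelling, but the pooling rule in 6.3 would still produce the mixture.

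A reader might infer that the primary safety endpoint is compromised or that every safety analysis is diluted. The documents do not support that. The by-group tables are intact, events summarised per subject are not affected in this way, all safety analyses are descriptive, Phase II enrolment depends on post-dose 1 data, and the only decision rule on pooled adjuvants (section 7) concerns ELISA GMT ratios.

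**Conclusion.** The point holds for two kinds of row in the pooled-by-adjuvant safety tables. Dose 2 is 67% PBS, and overall/dose is 33% PBS at Day 85 and 22% at the final analysis. These shares are exact on planned group sizes and follow from pooling whole groups while numbering doses by visit.

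The direction of bias rests on PBS being less reactogenic than vaccine. The reduction of the Dose 2 contrast to one third rests on equal PBS rates across classes. The percentages in the rate table are illustrations from assumed rates, not predictions.

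This should be corrected, because a stated rule gives rows that do not contain what their heading says. It is not critical: unmixed Dose 2 results remain available by group, and no decision depends on the pooled tables.

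**What to change.** In section 6.3, for the pooled-by-adjuvant versions of tables with dose rows (Templates 15–18 and 24, and any by-dose version of 19–20, which have no dose rows as mocked), state that:

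- the Dose 2 row uses only cH8/5/11-AS03, cH8/5/11-AS01 and cH8/5/11, about 47 subjects each;
- PBS recipients at Dose 2 are shown in a separate column (seven groups including IIV4, 7 × 47 = 329 subjects);
- pooled overall/dose is computed on non-PBS doses;
- IIV4 is not part of the no-adjuvant class.

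By-group overall/dose may stay as planned, since it describes the regimen as given. A footnote should say that it includes the PBS injection: 47/94 = 50% of doses at Day 85 and 47/141 = 33% at the final analysis in each group given PBS, against none in the cH8/5/11 groups.

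The cost is SAP wording and table programming, with no new data. Pooled Dose 2 columns fall from about 141 to about 47 subjects, so their confidence intervals widen, and those columns will match the by-group cH8/5/11 rows.

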#### **6.3.1. Analysis of safety planned in the protocol**

- The percentage of subjects with at least one local AE (solicited and unsolicited), with at least one general AE (solicited and unsolicited) and with any AE during the solicited follow-up period will be tabulated with exact 95% CI. The same calculations will be performed for AEs rated as grade 3.
- The percentage of subjects reporting each individual solicited local and general AE during the solicited follow-up period will be tabulated with exact 95% CI. The same tabulation will be performed for grade 3 AEs and for AEs with causal relationship to vaccination.

- The verbatim reports of unsolicited AEs will be reviewed by a physician and the signs and AEs will be coded according to the Medical Dictionary for Regulatory Activities (MedDRA). The percentage of subjects with at least one report of unsolicited AE classified by the MedDRA and reported up to 28 days after vaccination will be tabulated with exact 95% CI. The same tabulation will be performed for grade 3 unsolicited AEs and for unsolicited AEs with causal relationship to vaccination.
- The percentage of subjects with Medically Attended Event(s) (MAE(s)) will be summarized by group with exact 95% CI.
- The percentage of subjects with episode(s) of ILI will be summarized by group with exact 95% CI.
- At each hematology/biochemistry sampling timepoint, by study group, individual hematological and biochemical values will be presented as number of subjects out of range (above and below normal range) and tabulated by toxicity grading (refer to Appendix C of the protocol). In addition, changes from baseline (median/interquartile range) will be presented.
- SAEs and pIMDs will be described in detail. Withdrawals due to (S)AEs will also be summarized.

### **6.3.2. Additional considerations**

- In addition, the percentage of subjects with at least one local AE (solicited and unsolicited), with at least one general AE (solicited and unsolicited) and with any AE with causal relationship to vaccination during the solicited follow-up period will be tabulated with exact 95% CI. The same calculations will be repeated for grade 3 AEs with causal relationship to vaccination.
- The percentage of subjects reporting each individual solicited local and general grade  $\geq 2$  AE during the solicited follow-up period will be tabulated with exact 95% CI. The same tabulation will be performed for grade  $\geq 2$  and grade 3 AEs with causal relationship to vaccination, and for AEs with a medically attended visit.
- The overall number of days with symptoms will be summarized by dose and by symptom, using summary statistics.
- The percentage of subjects with at least one report of unsolicited grade 3 AE with causal relationship to vaccination reported up to 28 days after vaccination will be tabulated with exact 95% CI
- The percentage of subjects with at least one report of unsolicited AE requiring medical attention during the 28 days after vaccination will be tabulated with exact 95% CI. The tabulation will be repeated for the grade 3, related, and grade 3 related events. The same analysis will be provided for the events reported within 28 days post-vaccination.
- The percentage of subjects with episode(s) of grade 3 ILI (any, RT-PCR-confirmed) will be summarized by group with exact 95% CI.

- A summary of subjects with all combined solicited (regardless of their duration) and unsolicited AEs will be provided. Solicited AEs will be coded by MedDRA (using the latest version) as per the following codes:

Solicited symptom	Lower level term code
Pain at injection site	10022086
Redness at injection site	10022061
Swelling at injection site	10053425
Fever	10016558
Headache	10019211
Fatigue	10016256
Gastrointestinal symptoms	10017944
Arthralgia	10003239
Myalgia	10028411
Shivering	10040558

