- **Enrolment:** the study will follow a staggered enrolment with 2 steps; the first being Phase I (N = ~80) and the second being Phase II (N = ~390):
  - Phase I: During the Phase I enrolment, subjects will be vaccinated one at a time, at least 60 minutes apart, with a maximum of 10 subjects/day until ~80 subjects are enrolled (i.e. to obtain treatment groups of at least 8 subjects/group). If no safety issue is identified by the Independent Data Monitoring Committee (IDMC) upon review of the 7-day post-dose 1 safety data (Days 1-7) of all Phase I subjects (N = ~80), Phase II enrolment will be allowed to start.
  - Phase II: Subjects will be enrolled and vaccinated without limitation on the number of vaccinees per day or time between consecutive subjects.
- **Vaccination schedule:**
  - Two primary doses at Visit 1 (Day 1) and Visit 4 (Day 57).
  - A booster dose at Visit 8 (Month 14).
- **Definition of the different epochs:**
  - Epoch 001: Screening (Day -28 to -2) – only for Phase I subjects.
  - Epoch 002: Primary starting at Visit 1 (Day 1) and ending at Visit 7 (Month 8).
  - Epoch 003: Booster starting at Visit 8 (Month 14) and ending at Visit 12 (Month 26).

- **Intervals between study visits**

Interval	Optimal length of interval	Allowed interval**
Screening to Visit 1*	2-28 days	
Visit 1 → Visit 2	7 days	7-9 days
Visit 1 → Visit 3	28 days	28-38 days
Visit 1 → Visit 4	56 days	56-66 days
Visit 4 → Visit 5	7 days	7-9 days
Visit 4 → Visit 6	28 days	28-38 days
Visit 4 → Visit 7	168 days	168-196 days
Visit 4 → Visit 8	336 days	336-364 days
Visit 8 → Visit 9	7 days	7-9 days
Visit 8 → Visit 10	28 days	28-38 days
Visit 8 → Visit 11	168 days	168-196 days
Visit 8 → Visit 12	336 days	336-364 days

\* Only applicable for Phase I subjects. Screening evaluations may be completed 2 to 28 days before Day 1. Site staff should allow sufficient time between the screening and Day 1 visits to receive and review screening safety laboratory test results. If a delay occurs such that the interval between screening and the Day 1 vaccination exceeds 28 days, a re-screening visit should be scheduled before Visit 1.

\*\* Visits out of the allowed interval can lead to elimination from the Per-Protocol set for immunogenicity analysis.

- **Sampling schedule:**

- Blood samples for safety assessment will be drawn from all subjects at all visits: Screening\*, Days 1, 8, 29, 57, 64, 85, Month 8, Month 14, Month 14 + 7 days, Month 14 + 28 days, Month 20 and Month 26.

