## 4. ENDPOINTS

### 4.1. Primary endpoints

#### Reactogenicity and safety

- Occurrence of solicited local and general AEs after each vaccination:
  - Occurrence of solicited local AEs during a 7-day follow-up period (i.e. on the day of vaccination and 6 subsequent days) after each vaccine dose, in all vaccine groups.
  - Occurrence of solicited general AEs during a 7-day follow-up period (i.e. on the day of vaccination and 6 subsequent days) after each vaccine dose, in all vaccine groups.
- Occurrence of unsolicited AEs after each vaccination:
  - Occurrence of unsolicited AEs during a 28-day follow-up period (i.e. on the day of vaccination and 27 subsequent days) after each vaccine dose, in all vaccine groups.
- Occurrence of hematological and biochemical laboratory abnormalities after each vaccination:
  - Any hematological (red blood cells, white blood cells and differential count, platelets count and hemoglobin level) or biochemical (alanine aminotransferase, aspartate aminotransferase, creatinine, blood urea nitrogen [BUN] and BUN-to-creatinine ratio) laboratory abnormality at each visit subsequent to Day 1, in all vaccine groups.
- Occurrence of medically attended events (MAEs), potential immune-mediated diseases (pIMDs) and SAEs:
  - Occurrence of MAEs, pIMDs and SAEs throughout the entire study period, in all vaccine groups.

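### SAP 6.3.2 gives its two tabulations of medically attended events the same 28-day window, so no grade 3 or causality breakdown of these events is planned beyond 28 days after a dose

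*SAP*

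**What the plan says.** Section 4.1 of the current SAP (Amendment 3) separates two kinds of unsolicited safety endpoint. General unsolicited AEs are followed for 28 days after each dose. The second kind is followed for the whole study: "Occurrence of MAEs, pIMDs and SAEs throughout the entire study period, in all vaccine groups".

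Section 6.3.1 has one analysis of MAEs: "The percentage of subjects with Medically Attended Event(s) (MAE(s)) will be summarized by group with exact 95% CI". It states no window and no split by grade or causality.

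Section 6.3.2 adds, in a single bullet:
- a tabulation of subjects with at least one "unsolicited AE requiring medical attention during the 28 days after vaccination will be tabulated with exact 95% CI";
- its breakdowns: "The tabulation will be repeated for the grade 3, related, and grade 3 related events";
- a closing sentence: "The same analysis will be provided for the events reported within 28 days post-vaccination".

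The same bullet stands in all three earlier SAP versions, so it did not arise with the last amendment.

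**The concern.** A sentence that promises the same analysis for another set of events should change something, usually the period. Here nothing changes. A programmer must either produce the same tables twice or guess a window.

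The bullet also holds the only grade and causality breakdowns of unsolicited MAEs in the SAP text, and both of its windows stop at 28 days. The endpoint in 4.1 runs to the end of the study. SAEs and pIMDs share that endpoint and that period, and both have output showing intensity and causality without a 28-day limit. MAEs that are neither serious nor pIMDs do not.

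At stake is how well the report can describe later MAEs by severity and relatedness. If the window is settled only at the analysis stage, it is chosen after the unblinded interim analyses of section 8.1.

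**Working it through.** **Step 1: are the two windows really the same?** Both sentences run to 28 days after vaccination. The closing sentence might instead be read as covering all unsolicited AEs. It is then still redundant: 6.3.1 already plans 28-day tables for any, grade 3 and related unsolicited AEs, and another bullet of 6.3.2 adds grade 3 related ones. Neither reading gives a new table.

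**Step 2: what else in the SAP could give a later breakdown?**

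| Place | Period | Grade or causality shown? | Covers MAEs in general? |
|---|---|---|---|
| 6.3.1, MAE percentage | no 28-day limit | no | yes |
| 6.3.2, MAE bullet | 28 days | yes | yes |
| 6.3.2, grade 3 ILI | no 28-day limit | grade 3 | ILI only |
| Template 6 | no window | causality | only events leading to discontinuation |
| Templates 21 and 22 | no window | intensity and causality | only pIMDs, SAEs |
| Template 28 | whole study | related rows | only SAEs |
| Templates 19 and 20 | left open as a fill-in number of days | switches for both | no medically attended option in the title |

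What remains uncovered is an MAE that starts more than 28 days after a dose, is neither serious nor a pIMD, is not a grade 3 ILI and does not lead to discontinuation. Such an event counts in the overall percentage but has no planned severity or causality summary.

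**Step 3: how much follow-up time do the windows cover?** The SAP gives no figure of its own to reproduce. The inputs are the visit intervals in section 2 and the 28-day period in 4.1 (day of vaccination plus 27 days). All three vaccination visits are counted, including PBS at Day 57.

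- Follow-up = (Visit 1 to 4) + (Visit 4 to 8) + (Visit 8 to 12).
- Optimal intervals: 56 + 336 + 336 = 728 days.
- Windows: Days 1–28, 57–84 and 393–420. They do not overlap, so coverage is 3 × 28 = 84 days.
- Share covered: 84 / 728 = 11.5%. Not covered: 728 − 84 = 644 days, or 88.5%.
- Longest allowed intervals: 66 + 364 + 364 = 794 days; 84 / 794 = 10.6% covered, 89.4% not.

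With one analysis set to the entire study period, the breakdowns would cover 728 of 728 days.

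**The case against.** The strongest reply is that no stated endpoint goes unserved. The endpoint in 4.1 is occurrence, and 6.3.1 tabulates occurrence with an exact interval and no 28-day limit. The grade and causality repeats stand only under additional considerations, and nothing in the objectives or endpoints asks for them over the whole study. This stands. A reader might infer that the primary MAE endpoint goes unreported after Day 28, and the SAP does not support that.

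Second, the gap is narrower than it first looks. Late grade 3 ILI, events leading to discontinuation, SAEs and pIMDs all appear elsewhere. This also stands, and the point is limited accordingly.

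Third, the list of tables (TFL TOC) is a separate document that is not shown, and section 13 says templates are adapted as it directs. It may already list a whole-study MAE breakdown. That is possible, but the SAP wording would then disagree with the list and still need correcting.

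Fourth, the intended window is not stated. One of the two was probably meant to be the whole study, but this is inference. Deleting the duplicate sentence would also remove the redundancy, though not the gap.

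**Conclusion.** The point holds in a limited form. The second MAE analysis in 6.3.2 is empty as written. The SAP text also plans no grade 3, related or grade 3 related breakdown of MAEs beyond 28 days after a dose, although 4.1 defines MAEs over the entire study.

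The breakdowns cover 11.5% of follow-up time at optimal intervals and 10.6% at the longest allowed ones. It is tempting to read the remainder, about 88% to 89%, as the proportion of MAEs lost. The SAP does not support that: the figure is calendar time, the document says nothing about how events are spread over it, and every MAE still counts in the overall percentage. Nor does the SAP say that MAEs are followed throughout in order to detect delayed effects of the adjuvants, so the point does not rest on that.

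The conclusion assumes that all three vaccination visits open a 28-day window and that the TFL TOC adds no whole-study breakdown. Priority is low to moderate: a wording error with a modest gap in supplementary safety output.

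**What to change.** In 6.3.2, set one of the two MAE analyses to the entire study period, with the grade 3, related and grade 3 related repeats, and keep the other at 28 days after vaccination.

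Add a whole-study, medically attended run of Templates 19/20 alongside the 28-day runs. Do not reset the open day count in those shells to the whole study, because they must also produce the 28-day unsolicited AE tables. Align the TFL TOC with the new wording.

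The cost is one phrase of SAP text and a few extra table runs, by study group and again by pooled adjuvant as section 6.3 requires. No new data are needed, since the endpoint in 4.1 already calls for MAEs throughout the study.
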